| IMP accountability 1/5            |                              | ●              | ●                    | ●                          | ●   |   |
| Blood pressure (bp), seated                  |                              | ●              | ●                    | ●                          | ●   | ●   |
| Supply with bp device            |                              | ●              |                      |                            |   |   |
| Clinical chemistry               | ●                            | ●              | ●                    | ●                          | ●   | ●   |
| Cardiovascular outcome                       |                              |                | ●                    | ●                          | ●   | ●   |
| EQ-5D-5L                                     |                              | ●              | ●                    | ●                          | ●   | ●   |
| Check for imaging***/
upload if available |                              | ●              |                      | ● (at least once a year)   | ●   | ●   |

\*# Screening and baseline visit may be combined at just one visit, if verification of all inclusion and exclusion can be ensured at this visit, and the patient has ample time to consider participation.

\*\* (S) = study specific / (R) = Clinical routine

\*\*\* Either CTA or MRA as per standard of care (SOC), if new imaging is available

1 application of trial medication by patient at home once daily from day 0 to end of treatment; patients of intervention group only

2 applicable for females of childbearing potential only. Test must be repeated on Day 0 if result of initial test is not valid on Day 0 (depending on period/ menstrual cycle)

3 data on GFR and blood sodium in patients with pre-existing, compensated chronic renal failure, or other parameter such as INR, thrombocytes count, haemoglobin, if needed to confirm inclusion/exclusion criteria and/or if perceived necessary by investigator.

Data not older than 6 months from certified labs may be used.

4 applicable only if any SAEs have not been resolved at previous visits

5 applicable only for patients of intervention group

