### 5.4.2 Dosage Schedule

The study medication is given only to patients who have consented to study participation and who are randomized to the intervention group.

Maximum duration of treatment: 120 months  
Maximum dose allowed: 100mg ASA daily, orally

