### IMP Compliance

IMP accountability (supply and return) will be documented at each visit, according to the trial schedule. Respective numbers will be transferred in the CRF. Additionally, investigators must provide a statement regarding patients' over-all compliance at the end of the treatment.

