#### 5.4.5 Adjustments to dosage of the IMP in the individual trial subject

- A) The use of ASA may be interrupted, if a patient needs surgery during the course of the clinical trial. It will be resumed as soon as possible after surgery.
- B) No changes in IMP dosage are intended or permitted, even in case patients require a higher dose of ASA for other indications. However, if patients are medically required to be treated with higher doses of ASA (e.g. due to cardiovascular event) while being on treatment with the IMP, the treating physician can prescribe ASA as required and the IMP will be stopped for the time in which ASA is prescribed.
- C) For safety data, patients of the intervention group, who received concomitant long-term ASA will be analysed as per protocol, patients of the control group as ITT.

No further adjustments are planned.

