All patients will have a CTA/MRA at least 36 ( $\pm 6$ ) months after randomization and preferably around the last follow-up visit as per standard of care. All images will be uploaded in a pseudonymised manner to a central server. Patients will be told to stop the IMP if there is no indication to continue (indications to continue are for example myocardial infarction, TIA, ischemic stroke), and be advised to visit a general practitioner for future blood pressure regulation. A letter will be sent to the general practitioner that the study has ended.

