In addition to our main research question on the effect of combined ASA and blood pressure lowering therapy, a secondary aim is to study the effect of the blood pressure component of the combination therapy. For this aim we will accurately record who is using intensive blood pressure lowering therapy. Data of both the intervention and the control arms of PROTECT-U can be used for this purpose. For this research aim we will relate the intensive blood pressure lowering therapy usage percentage to the primary outcome. As this analysis pertains to a non-randomized comparison we need to adjust for potential confounding by other determinants of the primary outcome, including the other component (acetylsalicylic acid) of the combined treatment. Analyses will be done with multivariable Poisson regression in which we will model cumulative incidence of the primary outcome at three years.

We will do an additional analysis restricted to the patients randomized to the intervention group, because within this group detailed data on achieved blood pressure will be available obtained with a device that transmits blood pressure to a central post. For each patient we will calculate the percentage of time that systolic blood pressure is below 120 mm Hg. Then we will do an

analysis similar as described above in which we will relate the percentage of time that systolic blood pressure is below 120 mm Hg to the primary outcome, also adjusted for other determinants of the outcome.

Another secondary aim is to study the effect of ASA treatment alone. For these analyses, we will use data on drug accountability (for acetylsalicylic acid use). As these analyses pertain to non-randomized comparisons, we need to adjust for potential confounding by other determinants of the primary outcome, including the other component of the combined treatment. Analyses will be done with multivariable Poisson regression in which we will model cumulative incidence of the primary outcome at three years. These data will not be subject to an interim analysis.

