## 10 DATA MANAGEMENT

### 10.1 Data Collection

A study specific database will be set up using ClinCase™ and validated for this project with coded information of the participants who are included in the study. After informed consent, subjects will be registered in a secured database managed by the KKS using unique participant identification numbers. The patient ID is composed of a site number and the randomization number generated by the online randomizing tool. Only authorized study personnel will have access. Hence, the names and patient numbers of participants will be replaced by a study code for all study related procedures and will not be directly convertible to the participant. This code list is exclusively possessed by PI and investigators at each trial centre, and saved in a separate, secured database. All data will be collected according to the applicable national data protection, privacy and secrecy laws.

Study data collected in the e-CRF will consist of:

- Study characteristics: study number, date of randomization, treatment allocation.
- Data collected at baseline: date of birth, sex, history of hypertension / ischemic stroke / intracerebral hemorrhage / subarachnoid hemorrhage / myocardial infarction / peripheral vascular disease / polycystic kidney disease, medication use, tobacco smoking history including number of packyears of smoking and current number of cigarettes per day, alcohol use, recent (<6 months) GFR, number of first degree and second degree relatives with an intracranial aneurysm (either unruptured or ruptured), date and type of last aneurysm imaging before randomization, seated blood pressure, number of aneurysms, aneurysm size, aneurysm location, aneurysm shape, EQ-5D-5L.
- Data collected during the trial: smoking status, seated blood pressure, drug adherence (by counting unused tablets), occurrence of adverse events, concurrent medication, date(s) and type(s) of subsequent imaging, occurrence of aneurysm growth or rupture during trial according to local investigator, occurrence of cardio-/cerebrovascular outcomes during the trial, EQ-5D-5L.

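### The ASA-alone analysis takes ASA use from trial-tablet accountability, which misses ASA prescribed outside the trial supply in either arm

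*Protocol*

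**What the plan says.** Secondary objective A (Protocol 2.2) asks whether ASA lowers the risk of rupture or growth compared with no ASA. Section 9.3 answers it with a multivariable Poisson model for the three-year primary outcome, acknowledges that the comparison is not randomised, and says where ASA use comes from: "For these analyses, we will use data on drug accountability (for acetylsalicylic acid use". It names no other source.

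What accountability contains is set out elsewhere:

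- IMP Compliance (under 5.4.2): "IMP accountability (supply and return) will be documented at each visit, according to the trial schedule".
- Section 10.1 lists "drug adherence (by counting unused tablets" among the data collected during the trial.
- In the Clinical Trial Schedule, the accountability row carries a footnote reading "applicable only for patients of intervention group".
- Section 5.4.2 restricts study medication to consenting patients "who are randomized to the intervention group".

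Section 5.4.5 B deals with patients who need a higher ASA dose for medical reasons: "the treating physician can prescribe ASA as required and the IMP will be stopped for the time in which ASA is prescribed". Section 5.4.5 C foresees long-term ASA outside the trial supply in both arms, but its rule covers safety data only: "patients of the intervention group, who received concomitant long-term ASA will be analysed as per protocol, patients of the control group as ITT". Section 5.4.4 requires concomitant drugs to be recorded with type, dose, indication and duration, and the Schedule has concomitant medication at every visit.

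**The concern.** The source named in 9.3 measures trial tablets, whereas objective A is about taking ASA. The two differ in exactly the situations that 5.4.5 provides for. An intervention patient moved to prescribed ASA shows no tablet use while still taking the drug. A control put on ASA after randomisation leaves no trace in accountability at all.

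Two things are at stake. First, some ASA-treated person-time sits in the comparator, which pulls the estimate towards no effect. Second, if ASA exposure can be non-zero only in the intervention arm, it largely repeats allocation. The blood pressure target is also assigned by allocation, so the model has less with which to tell the two components apart. Controls on prescribed ASA would help to separate them, but this source cannot see them. Switched intervention patients recorded as untreated add variation that is partly false.

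Section 9.3 handles the other component differently: it promises to record actual use of intensive blood pressure lowering and to draw on both arms. Objective A has no randomised answer in this two-arm design, so this analysis is the planned answer.

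**Working it through.** **The plan's own figures.** The protocol gives no figure for the ASA-alone analysis. The effect assumed for ASA alone comes from 3.1: a 22.5% reduction, from 15% to 11.625%, so RR = 0.11625 / 0.15 = 0.775. With a two-sided alpha of 0.05, 80% power, pooled variance and no continuity correction, the main comparison (15% versus 8.25%, section 9.1) needs 353 per group, exactly as stated. The ASA-only design needs 1590 per group against the stated 1597, a difference below 1%. These inputs are therefore sound to work with.

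**Tracing exposure through the text.**

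| Patient | Truly on ASA? | What accountability shows |
|---|---|---|
| Intervention, taking IMP | yes | use |
| Intervention, IMP stopped under 5.4.5 B while ASA is prescribed | yes | no use for that time; earlier IMP still counts |
| Control, ASA prescribed after randomisation | yes | no record |
| Control, no ASA | no | no record |

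The last two rows cannot be told apart. Controls are either all read as unexposed or all read as missing. Daily ASA at entry is an exclusion (4.5), so only ASA started after randomisation matters.

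**Size, reading controls as unexposed.** Let *c* be the share of controls on prescribed ASA and *s* the share of intervention patients switched. Neither is given, so both are assumptions. With equal arms, the share of the apparently unexposed who really take ASA is

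f = (c + s) / (1 + s),

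and the apparent risk ratio is

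RR_obs = RR / (1 − f(1 − RR)).

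Example with c = 0.10 and s = 0.05: f = 0.15 / 1.05 = 0.143, and RR_obs = 0.775 / (1 − 0.143 × 0.225) = 0.775 / 0.968 = 0.801.

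| c | s | f | Apparent RR (true 0.775) | Apparent reduction (true 22.5%) |
|---|---|---|---|---|
| 2% | 0% | 2.0% | 0.7785 | 22.1% |
| 5% | 2% | 6.9% | 0.7872 | 21.3% |
| 10% | 5% | 14.3% | 0.8007 | 19.9% |
| 15% | 10% | 22.7% | 0.8168 | 18.3% |

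For a true RR of 0.70 (the 30% reduction also considered in 3.1), the first and last rows become 0.704 and 0.751.

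**What the formula leaves out.** It treats each misclassified patient as ASA-exposed for the full three years, which overstates dilution because a switch counts only from its start. It also gives everyone the same underlying risk. If switched patients have a higher risk of growth or rupture, placing them in the comparator raises its risk and exaggerates the benefit, against the dilution. If their risk is lower, dilution grows. The documents do not settle which applies.

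**Precision, for scale.** With 353 per group at 15% and 11.625%, SE(log RR) = √(1/41.04 − 1/353 + 1/52.95 − 1/353) = 0.194, so the unadjusted 95% interval around 0.775 is about 0.53 to 1.13. The shift in the table is small beside it.

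**The case against.** The strongest reply is that deriving an exposure variable is SAP work. Section 9.3 leaves final details to the SAP, nothing in it says that accountability is the only source, and concomitant ASA is recorded with dose and duration. The analysis is secondary and labelled non-randomised, and the shift is small beside its confidence interval. Most of this stands and limits the weight of the point. It does not remove it: the protocol has already named a source, and an SAP that follows the text would carry the error over.

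Several stronger readings are tempting and are not supported:

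- *Every intervention patient with a vascular event switches and then shows zero use.* Section 5.4.5 B covers only those needing a higher dose, and only while it is prescribed. Section 6.3 points the same way: at the end of treatment, "indications to continue are for example myocardial infarction, TIA, ischemic stroke", so some patients with such events may still be on the IMP.
- *The protocol codes controls on ASA as untreated.* It does not say so. This follows from using accountability alone, and missing is the other possibility.
- *The same variable adjusts the blood pressure analysis.* Section 9.3 says that analysis adjusts for ASA but names no source for it.
- *Much of the ASA effect is lost.* That would need a large share of low-accountability intervention patients to be switchers. The documents give no such share, and they do not describe the ASA analysis as confined to that arm. Borrowing the event rate of the blood pressure trial cited in 1.3 does not help: its patients were at increased cardiovascular risk, and its composite includes cardiovascular deaths, which start no ASA.

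**Conclusion.** The point holds as a defect in the exposure source stated for one secondary analysis. Followed as written, 9.3 misses ASA taken outside the trial supply in both arms and brings measured ASA exposure closer to allocation. On assumed shares of 2-15% of controls and 0-10% of intervention patients, a true RR of 0.775 would read about 0.78-0.82. That range assumes full-period exposure and equal underlying risk, and reads controls as unexposed. A reader might infer that the net bias is towards no effect. Dilution alone acts that way, but the switched patients' own risk could add to it or offset it, so the net direction is not established. The primary intention-to-treat comparison does not use this variable and is untouched.

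**What to change.** In 9.3, replace the single source with a definition that applies to both arms: ASA exposure is IMP use from accountability plus ASA recorded as concomitant medication (drug, dose, duration). State that time on prescribed ASA while the IMP is interrupted under 5.4.5 B counts as ASA-exposed. State also that the same variable is used wherever ASA is an adjustment factor in the blood pressure analysis, since the text is silent there. The SAP can carry the derivation, including how the short-term ASA use allowed by 5.4.4 is counted.

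The cost is protocol and SAP wording and some programming. The records are already collected at every visit in both arms, and nothing in patient management changes.

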#### *Cost-effectiveness analysis*

Cost-effectiveness will be studied by relating cost-differences between the intervention and comparator treatment to differences in number of patients who experience the primary outcome, i.e. cost per aneurysm growth or rupture prevented. It is anticipated that the low-cost intervention will prevent high-cost aneurysm ruptures and be cost-saving during the 3 year follow-up period. Furthermore, cost-utility will be assessed by studying cost differences between the two trial arms in relation to quality of life changes in patients. Quality of life will be measured 6-monthly using the EQ5D-5L questionnaire and QALYs will be estimated following the algorithm of Versteegh et al. 2016. Data on health care use, patient cost, and productivity losses will be elicited through the repeated administration (6-monthly) of standard questionnaires. Questionnaires will be distributed during outpatient visits of patients. Separate analyses for the German and Dutch data will be made, following either Dutch (Zorginstituut Nederland) or German (IQWiG) guidelines for economic evaluation. Data will be presented both from a health care and a societal perspective. Bootstrap methods will be used to present uncertainty around cost-effectiveness estimates using cost-effectiveness planes and acceptability curves. The economic evaluation will have a similar timeframe as the clinical study.

#### *Budget Impact Analysis (BIA)*

The design of the budget impact analysis (BIA) will be a study of different scenarios of either or not introducing preventive medication for patients with an aneurysm. The BIA will be based on data collected alongside the clinical study. It will allow estimation of the financial consequences of introduction of both ASA treatment and intensive hypertension control from the perspective of different stakeholders involved. All cost items needed for the BIA will be derived directly from our economic data collection, the valuation of those items depends on the perspective taken for the budget impact analysis. The perspectives to be included in the BIA are (1) net-BKZ or government perspective and (2) the health insurance perspective. Substitution effects, i.e. reduced need for expensive health care after aneurysm rupture will be taken into account. Different scenarios with different levels of implementation of preventive treatments will be analysed and compared, ranging from all patients with a known aneurysm, to patients with larger aneurysms only. The time horizon for the BIA will be 3 years. BIA results will be reported separately for each year within the time horizon and indexation will be applied.

Biometric analysis will be defined in the statistical analysis plan, which has to be authorised before opening the database by the biometrician, the sponsor, and the LKP.

The adjudication committee (PIs and another experts) will review protocol deviations and reach consensus on whether these should be regarded as major or minor, using blinded data if possible.

In addition, this committee will review unclear endpoints, such as sudden deaths and subarachnoid haemorrhage of unknown origin.

Subjects to be included in the analyses are all subjects randomised and thus a full intention to treat analysis.

The additional data provided by patients of the intervention group using blood pressure devices may be displayed in tables for descriptive statistics. They may be examined for their relationship with blood pressure values obtained during trial visits, for description of device utilisation, and for their relationships with outcomes as described above.

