## 2 TRIAL OBJECTIVES AND ENDPOINTS

### 2.1 Primary Objective and Primary Endpoint

The main purpose of this study is to assess the hypothesis that a strategy with a daily intake of low-dose ASA (81mg/day - 100 mg/day) and intensive blood pressure treatment (targeted systolic blood pressure below 120mmHg) with advice to patients to do weekly measurements using a home blood pressure measuring device reduces the risk of aneurysm rupture or growth compared with standard care (i.e. no ASA, blood pressure management according to guidelines which usually advise treatment if systolic blood pressure exceeds 140mmHg, and no home device for weekly blood pressure measuring).

The primary outcome measure will be aneurysm rupture or growth on serial imaging (MR- or CT-angiography). Aneurysm growth is defined as an increase in any aneurysm diameter by  $\geq 1$ mm within  $36\pm 6$  months from randomization. Aneurysm rupture or growth will be assessed centrally by two independent trial radiologists, who will be blinded to the treatment allocation. Events suspicious for SAH but negative CT-imaging will be reviewed centrally by the adjudication committee. Instances of sudden death of patients who died before reaching a hospital will be reviewed centrally by one neurosurgeon and two neurologists who are blinded to the treatment allocation to assess the (un)likelihood of SAH as cause of the sudden death.

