### 3 TRIAL DESIGN AND DESCRIPTION

#### 3.1 Trial design and justification of design aspects

This phase III multicenter, randomised, controlled trial with a PROBE design (prospective, randomised, open-label trial with blinded outcome assessment) is designed to assess whether a strategy with low dose ASA (81 mg/ day - 100mg/day) and intensive blood pressure treatment (targeted systolic blood pressure below 120mmHg) with weekly measurements using a home blood pressure measuring device reduces the risk of intracranial aneurysm rupture or growth, which is an established surrogate for the risk of rupture, compared with standard care (i.e. no ASA and blood pressure management according guidelines, which usually advise treatment if systolic blood pressure exceeds 140mmHg).

We will perform a phase III trial instead of a phase I/II trial since the protective effect of ASA on aneurysm inflammation or rupture was highlighted in a nested case-control study of UIA patients (n=1691) as well as in a small phase I trial randomising patients to ASA treatment or treatment as usual, which showed a significant reduction of radiological and histological aneurysm wall inflammation as surrogates for rupture. Further, the recent SPRINT study randomising 9361 patients to intensive versus standard BP treatment demonstrated a reduction of the primary composite outcome (myocardial infarction, other acute coronary syndromes, stroke, heart failure, or death from cardiovascular causes) without affecting the overall incidence of adverse or serious adverse events.

We chose an open-label design with observer-blinded outcome adjudication (by two independent neuroradiologists), because: a) a double or single-blinded study with predefined blood pressure targets would not be feasible, irrespective of the concomitant ASA treatment, b) to allow inclusion of UIA patients who are already treated for hypertension; and c) for pragmatic reasons, e.g. to not having to unblind treatment allocation for patients, who require a medical procedure potentially under ASA during the duration of the study (for at least 36±6 months after randomization). Also, due to very specific and well-known effects of ASA, it would be very likely to un-blind the patient by side effects.

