## 5.6 Blinding

This is an open trial, in which patients and investigators are not blinded. However, there will be an examiner-blinded assessment of images, therefore no information of patient allocation using patient ID-numbers or other data that would unblind the allocation of a patient to one of the two trial arms should be made available prior to the imaging analysis.

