#### 9.4 Interim Analyses

The DSMB will review data of two interim analyses on the primary outcome to assess the strength of the efficacy data. The first interim analysis will be carried out after 235 patients have had their 3-year outcome assessment; the second one after 470 patients have these outcome data. The DSMB will also check the assumptions for sample size calculations. The DSMB can recommend the Steering Committee of the PROTECT-U trial to:

- Adjust the sample size
- Early terminate the study when there is clear and substantial evidence of benefit, based on a significant (with alpha 0.1%) reduction in aneurysm growth and rupture (according to the Peto approach of interim analysis with alpha 5% at final analysis); a different stopping rule may be suggested by the DSMB.
- Early terminate the study when there is evidence of severe harm based on SAE reporting, outcome, and case fatality
- Early terminate the study in case accrual rates are too low to provide adequate statistical power for identifying the primary endpoint
- The Steering Committee and the DSMB will agree on the approach to early termination (stopping rules) and the statistical methods used for efficacy evaluation beforehand. This approach will be described in a separate DSMB charter.

After the inclusion of 100, 300 and 600 patients, and if needed after later time points, the proportion of patients with aneurysms <3 mm will be analysed. Patients in this subgroup have the lowest risk of aneurysm growth and rupture. Care should be taken that the proportion of patients with aneurysms <3 mm does not exceed 30% of the total study cohort, so that the power calculation is not jeopardized. With 776 patients to be included, no more than 230 patients with aneurysms <3 mm should be included.

Because the first formal interim analysis will take place after 235 patients reached the 36 months visit, an additional two preliminary interim analyses will be done based on the first 235 and 470 patients, at the timepoint 12 months after randomization of subject 235 and 470 respectively, with all routinely obtained follow-up data available. To this end local reports on aneurysm growth will be used.

Interim analysis reports will be prepared and supported by a member of the data management team of the KKS and then forwarded to the DSMB. The results will not be disseminated inside or outside the study team.

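### Blinded assessment is not secured for unclear primary events: sections 2.1 and 9.3 disagree on who judges sudden deaths, and two preliminary looks use local, unblinded growth reports

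*Protocol*

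**What the plan says.** The trial is a "prospective, randomised, open-label trial with blinded outcome assessment" (protocol 3.1). Section 5.6 adds: "This is an open trial, in which patients and investigators are not blinded". The main route to the primary endpoint is protected: "Aneurysm rupture or growth will be assessed centrally by two independent trial radiologists, who will be blinded to the treatment allocation" (2.1). Sections 5.6 and 6.2 require that image identifiers do not reveal the arm.

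Unclear events are handled in two places:
- Section 2.1, on people who die suddenly before reaching hospital: these cases "will be reviewed centrally by one neurosurgeon and two neurologists who are blinded to the treatment allocation".
- Section 2.1, on suspected SAH without CT confirmation: "Events suspicious for SAH but negative CT-imaging will be reviewed centrally by the adjudication committee".
- The end of section 9.3, printed after the budget impact text: "The adjudication committee (PIs and another experts) will review protocol deviations", and then "In addition, this committee will review unclear endpoints, such as sudden deaths and subarachnoid haemorrhage of unknown origin".

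In section 9.3 the use of blinded data, where possible, is attached to classifying protocol deviations as major or minor. It is not attached to endpoint review. Section 6.3 lets the same committee admit a same-modality pair of scans for patients with mixed imaging, who otherwise count as dropouts for the primary endpoint. It states neither criteria nor blinding for that decision.

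Section 9.4 plans two formal interim analyses on the primary outcome, after 235 and 470 patients have 3-year data. It adds two preliminary ones on the first 235 and 470 patients, 12 months after randomisation of subjects 235 and 470. For the preliminary ones: "To this end local reports on aneurysm growth will be used".

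**The concern.** An open-label trial with blinded assessment depends on the people who classify outcomes not knowing the arm. The central radiologists meet that for growth. They may have nothing to read for a death before hospital or a CT-negative suspected SAH, so those cases rest on clinical judgement, which is where knowledge of allocation can do most.

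The classification matters. Under section 9.3 a death from a cause other than rupture is censored, while a death judged to be SAH is a primary event. Section 9.4 also sends expedited notice of any SAH, with clinical data, to local PIs of all centres, so PIs on the committee may already know a case when they judge it.

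The scan-pair exception reaches growth as well: the reading is blind, but admission to the reading need not be.

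The preliminary looks raise a separate issue. Sites that know the arm report growth, and the board that receives those reports can recommend stopping for benefit or changing the sample size.

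**Working it through.** **Routes side by side**

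| Case | Decided by | Blinding stated | Section |
|---|---|---|---|
| Growth or rupture on imaging | Two central radiologists | Yes | 2.1 |
| Sudden death before hospital | Neurosurgeon and two neurologists | Yes | 2.1 |
| Sudden death, SAH of unknown origin | Committee including PIs | No | 9.3 |
| CT-negative suspected SAH | Adjudication committee | No | 2.1 |
| Same-modality scan-pair exception | Adjudication committee | No | 6.3 |
| Growth in the preliminary looks | Local reports | No; sites are open | 9.4, 5.6 |

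Rows two and three overlap for a sudden death before hospital, and the text does not say which governs.

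**The plan's sample size.** Inputs from section 9.1: 15% versus 8.25%, alpha 0.05 (taken as two-sided), power 80%. With pooled variance and no continuity correction:

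n = [1.96 × √(2 × 0.11625 × 0.88375) + 0.8416 × √(0.15 × 0.85 + 0.0825 × 0.9175)]² / 0.0675² = 353 per arm, as stated.

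**How much of the endpoint is exposed**
- Expected events: 353 × 0.15 + 353 × 0.0825 = 53.0 + 29.1 = 82.1.
- Section 3.1 puts the 5-year rupture risk below 3%. Assuming a constant rate, the 3-year risk is at most 1 − 0.97^(3/5) = 1.81%.
- Ruptures: at most 706 × 0.0181 = 12.8, or 12.8 / 82.1 = 16% of events. At least about 84% are therefore growth, read blind.
- Unclear SAH and sudden deaths are only a part of the ruptures. The protocol gives no figure for that part, nor for patients with mixed imaging.

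**What a few cases can do.** Suppose no true effect (15% in both arms, 353 each), and that knowledge of the arm removes k intervention-arm events. The number k is an assumption. The chance of a false significant benefit is 1 − Φ(1.96 − δ/SE), where δ = k/353, p₂ = 0.15 − δ and SE = √[(0.15 × 0.85 + p₂(1 − p₂))/353]. For k = 3: δ = 0.0085, SE = 0.0266, δ/SE = 0.32, giving 1 − Φ(1.64) = 5.1%.

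| k | 0 | 1 | 2 | 3 | 5 |
|---|---|---|---|---|---|
| False benefit | 2.5% | 3.2% | 4.0% | 5.1% | 7.7% |

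The ceiling for all ruptures in one arm is 353 × 0.0181 = 6.4, so k = 5 would be nearly all of them and is an extreme case.

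**Preliminary looks, if the 0.1% rule applied to them.** Assume no true effect, a 12-month growth risk of 5-10%, and local reading that under-calls intervention-arm growth by 10-40%. The chance of crossing for benefit is Φ[(d − 3.29 × SE₀)/SE₁], where d is the difference in reported risk and SE₀ and SE₁ are its pooled and unpooled standard errors. Worst case at 470 patients (235 per arm, 10% versus 6%): Φ[(0.04 − 3.29 × 0.0250)/0.0250] = 4.5%.

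| Look | No bias | Range over the assumptions |
|---|---|---|
| 235 patients | 0.05% | 0.09-1.5% |
| 470 patients | 0.05% | 0.12-4.5% |

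The data source matters more than the number of looks. Without bias, adding two looks at 0.1% moves the simple sum of alphas only from 5.2% to 5.4%.

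**The case against.** A reader might infer more than the documents support, in four ways.

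- *That blinded assessment fails as a whole.* It does not. Growth is at least about 84% of expected events on the assumption above and is read centrally and blind. Nothing sends local growth reports into the final analysis.
- *That the committee consists of unblinded PIs.* It is PIs and other experts, and blinding of its endpoint review is unstated, not denied. The sudden-death wording also differs in scope: section 2.1 covers deaths before hospital, section 9.3 sudden deaths generally.
- *That the committee's major/minor deviation calls shift the primary result.* They hardly can. Section 9.3 commits to a full intention-to-treat analysis, and section 9.2 allows exclusions only for objective, pre-randomisation eligibility violations under equal scrutiny.
- *That two of four looks at the primary outcome use unblinded data.* Only the two formal looks are described as being on the primary outcome. The preliminary ones come too early to be 36-month looks for most patients, and the 0.1% rule is not expressly attached to them. Stopping rules are left to a separate charter that is not at hand, and results are not to be disseminated. Under modest bias the chance of a false stop stays small.

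All four limits stand. They leave the conflict over sudden deaths, the missing blinding statement for the committee's endpoint and scan-pair work, and the silence on whether a look based on local reports may lead to stopping or resizing.

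**Conclusion.** The point holds in a limited form. Sections 2.1 and 9.3 conflict on who judges a sudden death before hospital. For unclear SAH and scan-pair exceptions, the protocol names a committee without stating that it is blind. The exposure is a part of at most about 13 ruptures among 82 expected events, plus an unknown number of scan-pair admissions. The 13 rests on a constant rupture rate and on taking the under-3% figure at its upper limit in both arms. One to three reclassified events would take the one-sided error from 2.5% to 3.2-5.1%; that number of events is assumed, not documented.

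The preliminary looks matter only if they can change the trial, which section 9.4 leaves open. The board's recommendations should not rest on unblinded readings when pseudonymised scans are already uploaded for central reading.

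**What to change.** - **Sections 2.1 and 9.3:** reconcile them so that every sudden death and every unclear or CT-negative suspected SAH goes to the blinded panel already named in 2.1.
- **Section 6.3:** state that scan-pair exceptions are decided blind to allocation and before the images are read.
- **Section 9.4 and the board's charter:** either use central blinded readings of the uploaded scans for the preliminary looks, or state that looks based on local reports cannot trigger an efficacy stop or a sample-size change.

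The cost is wording. The panel, the image server and the central readers already exist. The downside is that some central readings are done earlier, or that the preliminary looks serve safety only. No sample-size change follows.
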